2.4 FOLLOW-UP

Number of DFS events per person-year of follow-up is calculated at each DSMC review time to guide the timing for the database lock. The data cut-off is planned for prior to November 1, 2016 when we expect the number of DFS events will reach the target of 647 for the analysis with database lock in Q1 2017. Data as of the database cut-off will be used for analysis.

Median follow-up is calculated from the Kaplan-Meier estimate of overall survival, with the event/censoring indicator inverted (i.e. alive as event and dead as censored).

Updated results will be presented every two to three years thereafter.

2.5 TESTS AND ESTIMATES

The primary endpoint, DFS, will be compared between treatment arms using a two-sided stratified logrank test with an overall experiment-wise alpha-level equal to at most 0.05. The test statistic and p-value will be taken from the stratified Cox PH model score test. Hazard ratios will be estimated from a stratified Cox PH model, with 95% CIs. Kaplan-Meier estimates of the DFS distributions will be calculated for each of the treatment arms, with reporting of the 5yr DFS. We will check the proportional hazards assumption by visually assessing the plot of log(-log(survival)) versus log of survival time for parallelism. This will be done overall, and according to strata.

2.5.1 Stratification

The stratification factor during randomization is prior SERM/AI endocrine therapy (SERM(s) alone, AI(s) alone, both SERM(s) and AI(s)) as reported on randomization (RA) form. Institutions were balanced using dynamic balancing. Logrank test and Cox PH model will be stratified by prior SERM/AI endocrine therapy.

Note about values of strata as provided at randomization vs. actual values: The randomization form (RA form) collects the values entered into the IBCSG randomization system and used for stratification of the randomization assignment. If these values are incorrect then they are amended on the Registration form (A-form). We will cross-tabulate the stratification variables

between RA and A forms to compare the information obtained at randomization versus that on the A forms. For primary and secondary overall analyses we will use the stratification factor entered on randomization form. For subgroup analyses, we will use the actual values entered in the A form when available.

2.6 ANALYSIS COMPONENTS

2.6.1 Enrollment, Eligibility, Follow-up Compliance

This section summarizes accrual, eligibility, exclusions from ITT population, institutional CRF and follow-up compliance.

2.6.1.1 All randomized patients

Tables:

- Enrollment by group/country (rows), according to year and prior endocrine therapy strata (columns)
- Patient randomization treatment assignment and prior endocrine therapy strata
- Institutional follow-up compliance by group/country (rows)
- Case report form submission status (baseline forms)

Figures:

- Enrollment over time; x-axis time in 6-monthly intervals; y-axis number enrolled

2.6.1.2 CONSORT

In the manner of the CONSORT diagram, the following will be summarized.

Tables:

- CONSORT diagram content numbers by treatment assignment
 - Number of patients randomized
 - Number of patients included vs excluded from analysis population, with reasons
 - Listing of patients excluded from analysis population (patid, randomizing institution, randomization date, reason excluded, treatment assignment)
 - Number in analysis population who never started protocol treatment
 - Number in analysis population who WC/LFU
 - Number of patients analyzed in analysis population [same/as number included]

2.6.1.3 Analysis population

Tables:

- Enrollment by group/country (rows)
- Patient randomization assignment and prior endocrine therapy strata

- Eligibility status and reasons ineligible, overall and by treatment assignment
- Listing of ineligible patients (patid, randomizing institution, randomization date, reason ineligible, treatment assignment)
- Withdrawn consent and lost to follow-up status

2.6.2 Patient, Disease and Prior Treatment Characteristics

Characteristics of the analysis population will be summarized overall and by treatment group. Continuous variables are summarized as mean, SD, min/max, and quartiles. Categorical variables are summarized as N(%); for variables with unavailable (missing, unknown, not done) values, the default approach is to include an unknown category that is included in the denominator for percentages (rather than just listing the number of unknowns as a category).

Tables (overall and by treatment group, unless otherwise specified):

- Patient:
 - Age at randomization (continuous; categorized in 5-year intervals)
 - Race/ethnicity
 - Performance status at randomization
 - BMI at randomization
 - Menstruation status at primary cancer diagnosis
 - Symptoms (from baseline AE form)
- Treatment:
 - Local therapy (combining surgery [Mx/BCS] and radiotherapy [yes/no])
 - Chemotherapy (whether used; regimen [anthracycline-based; taxane-based; both; other])
 - Biologic therapy
 - Prior endocrine therapy and years of prior endocrine therapy
 - Duration from end of prior adjuvant therapy to randomization
- Disease:
 - ER/PgR status and details (H form)
 - HER2 status (H form)
 - Nodal involvement (number of positive lymph nodes 0-1, 2-3, 4-9, and 10+)
 - Tumor size (<1, 1-2, >2-5, >5 cm) and grade (1, 2, 3), primary histology (and other details from H form)
 - Disease laterality and location

2.6.3 Primary Efficacy Analysis

The primary efficacy analysis will proceed as summarized in Section 2.5 above. The data cut-off and database lock dates used for the analyses and the median follow-up duration will be reported.

2.6.3.1 Subgroup Analyses

The protocol pre-specified factors that will be used to characterize the patients enrolled in the study and to provide descriptive statistics of outcomes according to subgroups of the population. These factors include: age at randomization, body mass index, tumor size, tumor grade, number of positive lymph nodes, ER/PgR, HER2 status, type of prior endocrine therapy, duration of prior endocrine therapy by type, interval of time since the cessation of prior endocrine therapy till randomization. These analyses will be considered as secondary and descriptive.

The plans for these variables are summarized below:

- Age (5-year age groups (<55,55-59,60-64,65-69,≥70))
- BMI (obese (≥30), ~~normal or~~ overweight (25 - <30), normal (<25), unknown)
- ~~Chemotherapy (anthracycline-based, taxane-based, both, other, none)~~
- ~~Surgery/RT (Mx+RT; Mx alone; BCS+RT; BCS alone; unknown)~~
- Tumor size (≤2 vs >2 cm; unknown)
- Tumor Grade (1,2,3,unknown)
- ER/PgR subgroup (+/+; +/-; -/+; unknown and other):
- HER2 status (positive, negative, unknown)
- No. of positive lymph nodes (0, 1-3, 4+)
- type of prior endocrine therapy (AI, SERM, AI and SERM)
- duration of prior endocrine therapy (<4.5, 4.5-5.5, >5.5 years)
- Interval of time since the cessation of prior endocrine therapy till randomization (≤ 1 month, >1 month)

2.6.3.2 Models

Stratified Cox PH regression models will be used to: estimate HRs (95% CI) for treatment effect, adjusted for these covariates in Section 2.6.3.1; and estimate HRs (95% CI) for treatment effect within subgroups by including treatment-by-covariate interaction in the model (but not other covariates) and using contrasts.

2.6.3.3 Tables and Figures

Tables:

- Primary treatment comparison: N events and patients, HR, 95% CI, log-rank test statistic and p-value, 5yr DFS, SE and 95% CI

- Treatment effects within subgroups: N events and patients within each subgroup, treatment HR, 95% CI, p-value for test of treatment-by-variable interaction

Figures:

- KM plot of DFS, by treatment group, for entire analysis population (*y-axis: Percent Alive and Disease-Free; x-axis: Time since Randomization (12-month intervals); x-axis limited to 6 years (median follow-up plus 1 year) and numbers at risk at each 12-monthly interval*)
- Forest plot of DFS, overall and for subgroups

2.6.4 Secondary Efficacy Endpoints

Breast cancer-free interval, distant recurrence-free interval and overall survival will be summarized as described for DFS. Sites of first treatment failure will be summarized overall and by treatment group as N (%). Second (non-breast) malignancies as site of first failure, and deaths without prior cancer event will be summarized overall and by treatment group.

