2.2.4. Sites of first DFS failure

2.2.5. Second (non-breast) malignancies

2.2.6. Deaths without prior cancer event

2.2.7. Adverse events

### **3. Patient selection: criteria for patient eligibility/ineligibility**

#### **3.1. Patient characteristics**

3.1.1. Patients must be postmenopausal using any one of the following criteria. Because letrozole is not effective in pre- or perimenopausal patients, and may stimulate ovarian function, definitive confirmation of postmenopausal status is required.

- Patients of any age who have had a bilateral oophorectomy (including radiation castration AND amenorrheic for > 3 months)
- Patients 56 years old or older. If the patient has any evidence of ovarian function, biochemical evidence of definite postmenopausal status (defined as estradiol, LH, and FSH in the postmenopausal range) is required.
- Patients 55 years old or younger must have biochemical evidence of definite postmenopausal status (defined as estradiol, LH, and FSH in the postmenopausal range. Patients who have received prior LHRH analogue within the last year are eligible if they have definite evidence of postmenopausal status as defined above.

3.1.2. Patients must be accessible for follow-up.

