### 6.3. Other Events

#### 6.3.1. Second (non-breast) malignancy

Any positive diagnosis of a second (non-breast) malignancy other than basal cell or squamous cell carcinoma of the skin, cervical carcinoma *in situ*, or bladder cancer *in situ* is considered an DFS event and should be reported on the Follow-up Form (E) and on the Serious Adverse Event Forms (SAE-A and SAE-B).

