## 7.3. Serious Adverse Event (SAE) reporting

### 7.3.1. Definition

An SAE is defined in general as any undesirable medical occurrence/adverse drug experience that occurs during or within 30 days after stopping study treatment that, at any dose, results in any of the following:

- is fatal (any cause)
- life-threatening,
- requires or prolongs inpatient hospitalization,
- results in persistent or significant disability/incapacity
- is an unexpected grade 4 toxicity
- is a congenital anomaly or birth defect
- is a secondary (non-breast) malignancy

- requires significant medical intervention

Second (non-breast) malignancies are always considered SAEs, no matter when they are diagnosed. These events should be reported on the Serious Adverse Event Forms (SAE-A and SAE-B) and on the Follow-Up Form (E).

Other significant/important medical events which may jeopardize the patient are also considered serious adverse events.

Serious also includes any other event that the investigator or the IBCSG Safety Office judges to be serious or which is defined as serious by the regulatory agency in the country in which the event occurred.

An unexpected adverse event is one that is not listed as a known toxicity of the investigational drug in the summary of product characteristics.

A related adverse event is one for which the investigator assesses that there is a reasonable possibility that the event is related to the investigational drug. All adverse events judged as having a reasonable suspected causal relationship to the trial medication qualify as adverse reactions.

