## 9.2. Data analyses

The primary analysis will be undertaken with the intention-to-treat population of all randomized patients. The primary endpoint is disease-free survival (DFS: Section 6.1.1) and will be compared between treatment arms using a two-sided stratified logrank test with an overall experiment-wise alpha level equal to at most 0.05. Kaplan-Meier estimates of the DFS distributions will be calculated for each of the two treatment arms. Cox proportional hazards regression models will be used to investigate whether the treatment comparison is modified by adjustments for various covariates.

Other factors will be used to characterize the patients enrolled in the study and to provide descriptive statistics of outcomes according to subgroups of the population. These factors include age at randomization, body mass index, tumor size, tumor grade, number of positive lymph nodes, ER/PgR and HER2 status of the primary tumor, type of prior endocrine therapy, interval of time since the cessation of prior endocrine therapy. These analyses will be considered as secondary and descriptive.

The following secondary endpoints will be assessed: overall survival, distant disease-free survival, breast cancer-free interval, sites of first DFS failure, incidence of second (non-breast) malignancies, deaths without prior cancer event, incidence of targeted adverse events.

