2.3.2 Secondary Endpoints

- Overall survival (OS) is defined as the duration of time from randomization to death from any cause, or is censored at the date last known alive. (Note, for patients who withdrew consent or were lost to follow-up but follow-up for survival was possible through hospital or registry records, OS is censored at the date last known alive rather than date of last follow-up/withdrawn consent).
- Distant disease-free survival (DDFS) was a secondary endpoint in protocol. It will be replaced by a more modern definition -- distant recurrence-free interval (DRFI) defined as the duration of time from randomization to the first indication of invasive breast recurrence at a distant site. In the absence of an event, DRFI is censored at the date of last follow-up or date of death without distant recurrence.
- Breast cancer-free interval (BCFI) is defined as the duration of time from randomization to the first indication of the following events: invasive breast recurrence at local, regional or distant sites; a new invasive cancer in the contralateral breast. In the absence of an event, BCFI is censored at the date of last follow-up or date of death without prior breast cancer event. (Second non-breast malignancies are ignored)
- Site of First Failure: Hierarchy of failures from least to worst, following standard IBCSG definition:
 - o Local
 - o Contralateral Breast
 - o Regional ± above
 - o Soft Tissues/Distant Nodes ± above
 - o Bone ± above
 - o Viscera (including 'other') ± aboveas well as incidence of 2nd (non-breast) malignancy, death without prior cancer event, and adverse events.

For “site of first failure,” if there are 2 or more failure sites within 2 months of each other, then the “worst” site is considered as the site of first failure. For example if there is a regional recurrence and a bone recurrence within 2 months of each other, then the bone would be

considered the “worst” site of failure and considered as “site of first failure.” If second malignancy is coincident with breast cancer recurrence then site of first failure is considered as the breast cancer recurrence.

Per IBCSG standard, the date of DFS event is the date a proven recurrence was first suspected. In rare cases that the date suspected is prior to randomization, date of randomization is considered as date of event.

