2.6.4.1 Tables and Figures

Tables:

- Primary treatment comparison for each of the 3 secondary endpoints: N events and patients, HR, 95% CI, log-rank test statistic and p-value, 5yr DFS, SE and 95% CI
- Sites of first failure, overall and by treatment group
- Types of second non-breast malignancies, as site of first failure, overall and by treatment group.
- Death without recurrence (list of patients with cause of death)

Figures:

- KM plots of BCFI, by treatment group, for entire analysis population (*y-axis: Percent Free from Breast Cancer; x-axis: Time since Randomization (12-month intervals); x-axis limited to 6 years (median survival plus 1 year) and numbers at risk at each 12-monthly interval*)
- KM plots of DRFI, by treatment group, for entire analysis population (*y-axis: Percent Free from Distant Recurrence; x-axis: Time since Randomization (12-month intervals); x-axis limited to 6 years (median survival plus 1 year) and numbers at risk at each 12-monthly interval*)
- KM plot of OS, by treatment group, for entire analysis population (*y-axis: Percent Alive; x-axis: Time since Randomization (12-month intervals); x-axis limited to 6 years (median survival plus 1 year) and numbers at risk at each 12-monthly interval*)

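### The SAP tabulates second (non-breast) malignancies only as first failures, although the protocol endpoint is their incidence, and it does not say that the endpoint was narrowed

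*SAP*

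**What the plan says.** Protocol 2.2 lists sites of first DFS failure as item 2.2.4 and then, as a separate item, "2.2.5. Second (non-breast) malignancies". Protocol 6.1.2 keeps the same separation. Protocol 9.2 names what will be assessed: "incidence of second (non-breast) malignancies, deaths without prior cancer event, incidence of targeted adverse events". In that list the deaths are limited to those without an earlier cancer event; the malignancies carry no such limit.

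Protocol 6.3.1 defines the event broadly, starting from "Any positive diagnosis of a second (non-breast) malignancy other than basal cell or squamous cell carcinoma of the skin" and adding two in situ exceptions. Protocol 7.3.1 sets the reporting rule: "Second (non-breast) malignancies are always considered SAEs, no matter when they are diagnosed". Reports go on Form E and the SAE forms.

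SAP 2.6.4 restricts the analysis: "Second (non-breast) malignancies as site of first failure, and deaths without prior cancer event will be summarized overall and by treatment group". The table list in SAP 2.6.4.1 does the same: "Types of second non-breast malignancies, as site of first failure, overall and by treatment group". SAP 2.3.2 adds a tie rule: "If second malignancy is coincident with breast cancer recurrence then site of first failure is considered as the breast cancer recurrence".

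**The concern.** The protocol asks how many patients developed a second malignancy. The SAP outputs answer a different question: how many had one as their first DFS event. A patient whose second cancer follows a breast recurrence, or coincides with it, belongs to the first count and not to the second.

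Two things follow. A named secondary endpoint would be reported on a narrower definition without the reader being told. And whether a malignancy is counted depends on whether a breast event came first, so an effect of the regimen on recurrence could in principle carry over into the second-malignancy comparison.

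**Working it through.** **Is the any-time count planned elsewhere?**

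- DDFS in Protocol 6.1.2 included second malignancies. SAP 2.3.2 replaces it with DRFI, which does not, and BCFI ignores them.
- They are not on the targeted adverse event list (Protocol 7.1, legend C).
- They are not among the four late adverse event categories in SAP 2.6.5.3.
- The write-in table of other grade 3 or higher events rests on adverse event forms that, under Protocol 8.1, are submitted at baseline and during letrozole only.

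So no planned table gives the incidence. SAP 2.3.2 states openly that DDFS is replaced; it says nothing comparable here.

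**Direction.** By construction, first-failure count = all patients with a second malignancy − those after a breast event − those coincident with one. Neither subtracted term can be negative.

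**Design figures.** The documents give no second-malignancy figure to reproduce. The design figures do reproduce: 0.90^0.80 = 0.91917, as stated. Schoenfeld's formula gives 4 × (1.960 + 0.842)² / (ln 0.80)² = 631 events for a fixed design, and 646.6, hence 647, with Lan-DeMets O'Brien-Fleming looks at 40% and 70%. The point does not depend on them.

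**Size (illustration).** Inputs from the documents:

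- 4884 patients (SAP 1.2), taken as 2442 per arm.
- First and last randomization on 5 December 2007 and 8 October 2012 (SAP 1.2) and cut-off by 1 November 2016 (SAP 2.4), so about 4.1 to 8.9 years of potential follow-up, taken as uniform with no loss.
- 4-year DFS of 90%, and 91.8% in node-positive MA.17 patients when only breast events count (Protocol 9.3).

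Hazards per year: all DFS events λ = −ln(0.90)/4 = 0.0263; breast b = −ln(0.918)/4 = 0.0214; other = 0.0050.

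Assumed: second malignancies are 40 to 60% of the other events, at the same hazard s before and after relapse; mortality after relapse μ is 0.05 to 0.35 per year; HR 0.80 applies to breast events only. With k = μ + s, over follow-up F:

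- first = s(1 − e^(−λF))/λ
- later = [s·b/(k − λ)] × [(1 − e^(−λF))/λ − (1 − e^(−kF))/k]

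Example, continuous arm, 40% share, μ = 0.20, F = 6.5: s = 0.00198 and k = 0.20198. First = 0.00198 × 5.974 = 0.01183, or 28.9 patients of 2442. Later = 0.000241 × (5.974 − 3.619) = 0.00057, or 1.4 patients.

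Averaged over follow-up, with both arms added, and repeated with shares set directly as fractions of the continuous arm's DFS hazard (second malignancy / breast / death):

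| Second-malignancy share | First | Left out, μ = 0.05 | Left out, μ = 0.20 | Left out, μ = 0.35 | Arm difference in left-out cases |
|---|---|---|---|---|---|
| 40% of other events | 58.0 | 3.4 (5.6%) | 2.5 (4.2%) | 2.0 (3.3%) | 0.2 to 0.4 |
| 60% of other events | 87.0 | 5.2 (5.6%) | 3.8 (4.2%) | 3.0 (3.3%) | 0.3 to 0.6 |
| 15 / 75 / 10% of DFS events | 115.6 | 6.3 (5.2%) | 4.7 (3.9%) | 3.6 (3.0%) | 0.4 to 0.7 |
| 25 / 60 / 15% of DFS events | 192.4 | 8.4 (4.2%) | 6.2 (3.1%) | 4.8 (2.4%) | 0.5 to 0.9 |

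Most cells lie between 3 and 6%; the lowest corner is 2.4%. If HR 0.80 is applied to every DFS component instead, the arm difference reaches 1.6 patients in the most extreme cell, but the true incidence then differs between arms too, so that gap is not an artefact of counting alone. Coincident cases would add to the shortfall; the documents give no basis for estimating them.

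**The case against.** The protocol never says that second malignancies are counted at any time. It lists them between two items tied to first events, and Protocol 6.2 and 6.3.1 treat them as a form of failure and a DFS event. Reading the item as the second-malignancy component of DFS is therefore possible, and the SAP labels its table honestly. On that ground a reader should not infer that the planned number is wrong: it is right for what it claims to be. What stands is that Protocol 9.2 says "incidence of second (non-breast) malignancies" without a first-event limit, places it beside an endpoint that has one, and requires reporting at any time. If a narrower definition was meant, neither document says so. SAP 2.3.2 also mentions the incidence of second malignancy after the site-of-failure hierarchy, but the layout of the text leaves unclear whether that is a separate endpoint, so little weight rests on it.

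A reader might also infer that later malignancies are never counted. The documents do not support that. The DSMC reviews second malignancies every six months (SAP 1.5), SAE summaries are issued monthly (Protocol 7.3.3), and a case on treatment can appear among the write-in events. The tie rule classifies site of failure and deletes nothing from the data. The accurate statement is that no planned table gives the endpoint.

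Finally, an any-time count does not remove all dependence on recurrence, because death after relapse shortens the time at risk. That is true, and it is a reason to keep the first-failure table beside the new one.

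**Conclusion.** The mismatch between protocol and SAP is real, minor and cheap to close. The planned outputs omit known cases of a named secondary endpoint, in one direction only, and without announcing the change. The likely size is about 3 to 6% of second malignancies, roughly 2 to 9 patients, plus coincident cases. That range rests on constant hazards, planning-stage event rates, assumed second-malignancy shares, an assumed mortality of 5 to 35% per year after relapse, and an unchanged second-malignancy hazard after relapse; none of the last three is given in the documents.

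A reader might go further and infer that a treatment effect on recurrence materially distorts the comparison of second malignancies. The figures do not support this: with the effect confined to breast events, the arms differ by less than one patient in the number left out, and SAP 2.6.4 only summarizes this endpoint. DFS counts the first event whatever its type, so the primary analysis and the 647-event target are untouched.

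**What to change.** Keep the first-failure table as a description of DFS components. Add one table of all second (non-breast) malignancies from randomization to data cut-off, by type and arm, whether or not a breast event came first or at the same time, drawn from Form E and the SAE forms. Cumulative incidence with death as a competing event is an optional addition. If the sponsor did intend first events only, SAP 2.3.2 should say that the endpoint was narrowed and why, as it does for DDFS. The cost is one table or one sentence; no new data are needed.
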